### 308 3.4 Interventions

309 Details on the specific treatments included for each virus are described in virus specific  
 310 annexes.

311 **3.5 Study outcomes**

312 **3.5.1 Primary outcome**

- 313
  - All-cause mortality at 28 days following randomisation

314 **3.5.2 Secondary outcome**

- 315
  - Time (days) to *Filovirus* RNA <LLOQ (lower limit of quantitation) within 28 days

316 [Viral clearance, using results from study or routine clinical samples, is defined as

317 the first negative *Filovirus* RT-PCR test without a subsequent positive test result

318 or subsequent death. In the unlikely scenario that a patient is discharged home

319 without two successive negative RT-PCR tests, the date of the first negative test

320 or, if there is no negative test result, the date of medical discharge will be used.]

321 **3.5.3 Other outcomes**

- 322
  - Viral load (measured by cycle threshold) on blood samples taken at Day 3, 5, 7

323 and 10.

324 
  - Progression of organ dysfunction, measured on blood samples taken at Day 3, 5,

325 7, 10.

326 **3.5.4 Safety outcomes**

327 In addition to study outcomes (e.g. mortality), Adverse Events will be recorded if they fall

328 into one of the following groups:

329

- 330 a. Adverse Events of Special Interest (AESIs; e.g. infusion-related reactions).
- 331 b. Serious Adverse Events that are **not considered to be due to the underlying *Filovirus***
- 332 **infection.**
- 333 c. Serious (per standard regulatory definition) that are considered with reasonable
- 334 probability to be related to one of the study medications (i.e. Suspected Serious
- 335 Adverse Reactions, which includes Suspected Unexpected Serious Reactions
- 336 [SUSARs]).
- 337

338 Pregnancy and foetal outcomes will also be recorded.

339

340 Study outcomes will be assessed based on data recorded up to the time of death, hospital

341 discharge or 28 days after randomisation (whichever occurs first). Pregnant women will be

342 followed up to completion of pregnancy.

343

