### 351 4.1 Main analysis approach

352 For all each randomised comparison, the outcomes will be made between all participants  
353 randomised to the different treatment comparisons, irrespective of whether they received  
354 some, none, or all of their allocated treatment (i.e. these comparisons will be based on  
355 “intention-to-treat” analyses).

356 The primary analyses will involve pairwise comparisons between the active ‘experimental’  
357 and ‘reference’ arms as follows:

- 358 • Effect of monoclonal antibody: monoclonal vs. no additional treatment.
- 359 • Effect of antiviral: antiviral vs. no additional treatment.
- 360 • Effect of host-directed therapy: host-directed therapy vs no additional treatment.

361 Logistic regression adjusted for baseline levels of key prognostic factors will be used to  
362 estimate the conditional odds of 28-day mortality for each treatment group relative to its  
363 control (ie, the 28-day conditional odds ratio) and its 95% confidence interval. A two-tailed  
364 P-value <0.05 will be considered as statistically significant. Logistic regression (based on  
365 vital status at Day 28, regardless of the time to death within this 28-day range) will be used  
366 in preference to Cox regression because the latter might give undue weight to the exact  
367 times of death of the very poor-prognosis patients (thereby giving inadequate weight to the  
368 death or survival of the better-prognosis patients). However, for illustrative purposes,  
369 Kaplan-Meier plots showing the pattern of survival over the first 28 days will also be created,  
370 both overall and within prognostic categories. For the primary objective of assessing the  
371 effects of each study treatment on 28-day mortality, discharge alive before day 28 will be  
372 assumed as survival to day 28 (unless there are additional data confirming otherwise).

373 For the secondary objective of assessing the effects of each treatment on time to filovirus  
374 RNA <LLOQ within 28 days, differences in median days to filovirus RNA <LLOQ will be  
375 tested using the Wilcoxon rank-sum test, imputing deaths prior to day 28 as the worst ranks,  
376 with earlier deaths having a worse rank than later deaths. The study will collect viremia data  
377 at baseline and approximately days 3, 5, 7, 10. Patients who are discharged from inpatient  
378 care but without an available *Filovirus* RT-PCR test result will be assumed to have *Filovirus*  

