#### 431 4.2 Sample size estimation

432 The larger the number randomised, the more accurate and informative the results will be  
433 and, over time, the more potential treatments can be assessed. However, it is not possible  
434 to make precise sample size estimates in the context of an outbreak where there are many  
435 unknowns. The numbers required will be influenced by many factors, including the case  
436 fatality and speed of presentation and diagnosis at a clinical facility, changes in usual  
437 standard of care, and how much the proportional reduction in mortality differs between  
438 better-prognosis and worse-prognosis patients.

439 Ideally, each comparison should be sufficiently large to provide good power (e.g. 90% power  
440 to achieve  $2P=0.01$ ) to detect a proportional reduction in mortality of at least one third. This  
441 may require randomisation of several hundred patients in each comparison. For example, if  
442 mortality in the reference arm was 50%, randomisation of around 520 participants in  
443 a single comparison would give more than 90% power at  $2P=0.01$  to detect a proportional  
444 reduction in mortality of one-third and more than 80% power at  $2P=0.05$  to detect a smaller  
445 (but still useful) reduction in mortality of one-quarter. (Note that with 50% mortality in the  
446 reference arm, the above mortality risk reductions of one-third or one quarter would  
447 represent mortality odds reductions of, respectively, one-half or two-fifths.)

448 However, it is possible that any single outbreak might end before the trial has recruited such  
449 numbers during that outbreak, or in some instances, that availability of some of the study  
450 interventions will limit enrolment. Even these more limited numbers, perhaps from a single  
451 outbreak, might still deliver clear results and change clinical practice. Suppose, for example,  
452 that 120 patients were randomised between a monoclonal antibody plus usual care vs. usual  
453 care alone. The primary analysis of the effects of adding the antibody to usual care would  
454 then be based on only 60 vs 60 patients, far fewer than ideally needed. Nevertheless,  
455 suppose that the antibody reduced 28-day mortality from 30% to 10% in the better-prognosis  
456 half of all patients and from 90% to 70% in the worse-prognosis half (approximately as was  

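### Section 4.1 describes the secondary rank-sum test as a test of median days to viral clearance, but with deaths ranked worst it is a death-inclusive composite: at 50% reference mortality, death or its timing decides about 67–75% of comparisons

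*Protocol*

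**What the plan says.** Protocol section 3.5.2 lists a single secondary outcome, time in days to filovirus "RNA <LLOQ (lower limit of quantitation) within 28 days". Section 4.1 fixes its analysis: "differences in median days to filovirus RNA <LLOQ will be" "tested using the Wilcoxon rank-sum test, imputing deaths prior to day 28 as the worst ranks", "with earlier deaths having a worse rank than later deaths".

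The paragraph before, on the primary outcome, chooses logistic regression on day-28 vital status "in preference to Cox regression because the latter might give undue weight to the exact" times of death of patients with a very poor prognosis.

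Section 4.2 illustrates the size of a comparison with the case where "mortality in the reference arm was 50"%, and about 520 participants. Its second illustration has 60 v 60 patients, with mortality falling from 30% to 10% in the better-prognosis half and from 90% to 70% in the other, which averages 60% v 40%. Section 2.1 quotes case fatality of 36–65% for SUDV, usually 50–70% for EBOV, and 23–88% for Marburg, with the two largest Marburg outbreaks above 80%.

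**The concern.** There are three faults in text that the protocol itself fixes.

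1. The rank-sum test compares whole rank distributions. It does not in general test a difference in medians.
2. Once deaths hold the worst ranks, an arm has a median number of days to clearance only if fewer than half of its patients die. The diseases studied often exceed that.
3. Ordering deaths by day gives weight to exact death times. The paragraph before gives such weight as its reason for rejecting Cox regression, and no reason is offered for treating the two outcomes differently.

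What is at stake is interpretation. A significant result reported under the name of time to viral clearance could come from fewer deaths, or only from later deaths, with no virological effect.

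**Working it through.** **The plan's own figure first.** With 260 per arm and a normal approximation for two proportions:

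- 50% v 33.3% at 2P=0.01: pooled SE = √(2×0.4167×0.5833/260) = 0.0432; unpooled SE = 0.0426; z = (0.1667 − 2.576×0.0432)/0.0426 = 1.30; power 90.3%.
- 50% v 37.5% at 2P=0.05: z = (0.125 − 1.96×0.0435)/0.0432 = 0.92; power 82.1%.

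Both agree with section 4.2 (above 90% and above 80%). The 50% scenario is therefore taken as stated.

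**Where the median falls.** If mortality is p and deaths rank worst, an arm's median is the 0.5/(1−p) quantile of survivors' clearance times.

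| Mortality | 0.5/(1−p) | Meaning |
|---|---|---|
| 33.3% | 0.75 | 75th percentile of survivors |
| 37.5% | 0.80 | 80th percentile of survivors |
| 40% | 0.83 | 83rd percentile of survivors |
| 50% | 1.00 | boundary between slowest survivor and deaths |
| 60% | 1.25 | a death |
| 70% | 1.67 | a death |

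At 50% the reference median was a death or on the boundary in about 52–54% of simulated trials. In the 60 v 60 example, taking 30 reference patients in each half, expected deaths are 36 with SD √(30×0.3×0.7 + 30×0.9×0.1) = 3. The chance that more than half die is about Φ((36−30.5)/3) = Φ(1.83), or 97%. Even where both medians exist, arms with different mortality are compared at different percentiles of their survivors.

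**What decides the rank comparisons.** The statistic counts between-arm patient pairs. With mortality pc (reference) and pt (treated), the share decided by clearance is (1−pc)(1−pt), by one patient dying pc(1−pt)+pt(1−pc), and by day of death pc×pt.

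| pc v pt | Clearance | One dies | Day of death | Death or its timing |
|---|---|---|---|---|
| 50 v 50% | 25% | 50% | 25% | 75% |
| 50 v 37.5% | 31% | 50% | 19% | 69% |
| 50 v 33.3% | 33% | 50% | 17% | 67% |
| 60 v 40% | 24% | 52% | 24% | 76% |
| 30 v 20% | 56% | 38% | 6% | 44% |

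These shares need no distributional assumption.

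**Simulated rejection rates.** 260 per arm, 2,000 runs, two-sided 0.05 (stated for mortality, assumed here for the secondary outcome). Assumptions not in the documents: clearance day in survivors Normal(12, SD 4), death day gamma (mean 7, SD 4), all survivors clear by day 28. Mortality is 50% in both arms unless stated.

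| True effect | Deaths ordered (plan) | Deaths tied |
|---|---|---|
| None | 4.4% | 4.1% |
| Mortality 50→33.3% only | 91% | 93% |
| Mortality 50→37.5% only | 70% | 73% |
| Clearance 2 days faster only | 27% | 30% |
| Deaths 2 days later only | 33% | 5.4% |
| Deaths 4 days later only | 79% | 4.5% |

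Other assumed death-time distributions put the two-day delay at 37% and at 47–49% for the same 260 per arm, and at about 15–24% for 60 v 60.

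**The case against.** Ranking death worst is a recognised and valid way to handle an outcome cut off by death. It keeps every randomised patient, avoids conditioning on survival and holds type I error (4.4% above). Section 3.5.2 already excludes patients who later die from its definition of clearance, so the role of death is partly declared. Mortality is analysed separately as the primary outcome, viral load by Ct at days 3, 5, 7 and 10 is another listed outcome, and section 4.1.4 promises caution with secondary results. All of this stands, and it keeps the point from being severe.

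Several stronger readings are tempting but not supported:

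- *The median does not exist at 50% mortality.* It sits on the boundary and is unstable there; it fails outright only above 50%. The treated-arm median exists at the plan's target effects, and at 30% mortality both exist. Section 4.2 gives 50% only as an example.
- *The protocol commits to reporting a difference in medians.* It says that differences will be tested. It does not name the reported estimate.
- *Cox regression was rejected because death times are never admissible.* The reason concerns the mortality estimate. The conflict with ordering deaths here is real but is one of reasoning, not a breach of a general rule.
- *The 30%/90% strata show a larger timing effect at 520 patients.* Those strata belong to the 120-patient example.
- *Tying deaths cures the problem.* It removes the timing effect but leaves the dominance of mortality (91% v 93%, 70% v 73%).

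A delay that shifts every death and saves nobody is also a constructed case. It shows what the test responds to, not what is likely.

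**Conclusion.** The point holds in this form: the median wording in section 4.1 is wrong for the test named, and a difference in median days cannot be calculated whenever reference mortality exceeds 50%. That covers the plan's 60% v 40% example, most of the quoted EBOV range and the two largest Marburg outbreaks. At 50% reference mortality the result is governed about 67–75% by death or its timing. A significant result is therefore evidence on a composite, not on clearance. The pair shares and median positions follow from arithmetic alone. The rejection rates rest on the assumed distributions of clearance and death times, which the documents do not give, so the exact percentages should not be leaned on. Severity is moderate: the test is valid as a composite, and the primary outcome and sample size are untouched.

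**What to change.** In section 4.1, with matching text in the SAP, before any unblinding:

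1. Replace the reference to differences in median days with the Mann-Whitney win probability (the chance that a treated patient ranks better than a control patient, ties counting half) and its confidence interval.
2. Label the outcome a death-inclusive rank composite, so that a significant result is not reported as faster clearance.
3. Show beside it, by arm, the cumulative incidence of viral clearance to day 28 with death as a competing event. This curve also reflects survival, but it lets the reader see the two components.
4. Preferably give all deaths by day 28 one tied worst rank, or report that as a sensitivity analysis. If ordered deaths are kept as the main ranking, say why death timing is suitable here and not for mortality.

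The cost is a few sentences and no new data. Item 4 has a small downside, on which statisticians may differ: information on the timing of deaths leaves this test. It remains in the planned Kaplan-Meier plots.

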### 288 3.3 Randomisation

289 Randomisation will be between the following treatment domains in a factorial manner.

290 **Table 1. Randomisation domains.**

Domain	Filovirus x (e.g. SUDV)	Filovirus y ( e.g. EBOV)	Filovirus z (e.g. SUDV)
Randomisation 1 (monoclonal antibody/ies)*	Virus specific monoclonal antibody vs no additional treatment (1:1)	Virus specific monoclonal antibody vs no additional treatment* (1:1)	Virus specific monoclonal antibody vs no additional treatment (1:1)
Randomisation 2 (antiviral)	Antiviral vs no additional treatment (1:1)		
Randomisation 3 (host-directed)	Host directed therapy vs no additional treatment (1:1)		

291 \* Where a licensed monoclonal product exists e.g. MAb114 or REGEN-EB3 for EBOV, patients should receive  
 292 the licensed monoclonal product as part of usual care and would therefore not be randomised into the  
 293 monoclonal domain. However, in some circumstances randomization in this domain may occur (e.g. to test a  
 294 different dose vs. the licensed dose).

296 Randomisation will be done through use of an internet (or, where necessary, telephone)  
 297 based randomisation service. In an effort to prevent the impact of chance imbalances in key  
 298 baseline prognostic factors on the study results, randomisation will, wherever possible, be  
 299 performed with minimisation by such factors. Minimisation factors will be age strata  
 300 (children, younger adults, older adults), viral load, and outbreak. (Where this is not possible,  
 301 simple randomisation will be performed.)

302 If one of the treatments is not available at the site or not suitable for the individual patient  
 303 they will not be eligible for randomisation in that domain but remain eligible for randomisation  
 304 in the other domains. For example, if the monoclonal antibody is not available at the site,  
 305 then a patient may be randomised in the antiviral therapy (antiviral vs. no additional  
 306 treatment) and host-directed therapy (host-directed therapy vs. no additional treatment)  
 307 comparisons only.

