379 RNA <LLOQ on their day of discharge (unless in a particular case there is good evidence to  
380 the contrary).

381 For each treatment, the main comparisons will ignore any other treatments that the patient  
382 may have been randomised to in a factorial manner. However, subgroup analyses of each  
383 treatment effect will include analyses by such factorial treatments.

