#### 391 4.1.2 Adjustment for baseline characteristics

392 The main logistic regression analyses described above will adjust for important prognostic  
393 markers recorded at baseline (eg, age, RT-PCR Ct value, virus type, and time since  
394 symptom onset). This provides a safeguard against the impact that any chance imbalances  
395 in their frequencies between randomised groups may have on the randomised comparisons.  
396 In addition, even if there were no such imbalances, adjustment for baseline characteristics  
397 somewhat increases statistical power by ensuring that, effectively, better-prognosis patients  
398 are compared only with each other and that worse-prognosis patients are compared only  
399 with each other. [Exact details of the prognostic factors adjusted for in the logistic regression  
400 analyses will be provided in the SAP prior to any unblinded analyses being done.](#)

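### Section 4.1 has the main comparisons ignore the other randomised allocations: a valid analysis, but it gives up about one to two points of power if a co-randomised treatment works

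*Protocol*

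**What the plan says.** Section 3.3 sets up to three concurrent 1:1 comparisons: "Randomisation will be between the following treatment domains in a factorial manner". Section 4.1 specifies the primary model, "Logistic regression adjusted for baseline levels of key prognostic factors will be used to" estimate the odds of death by day 28 relative to "control (ie, the 28-day conditional odds ratio) and its 95% confidence interval", and adds that a two-tailed "P-value <0.05 will be considered as statistically significant". The same section then fixes how co-allocations are handled: "For each treatment, the main comparisons will ignore any other treatments that the patient" may have been randomised to factorially. They reappear only in subgroup analyses, where each "treatment effect will include analyses by such factorial treatments".

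Section 4.1.2 gives two reasons for covariate adjustment. It guards against chance imbalance, and even without imbalance it "somewhat increases statistical power by ensuring that, effectively, better-prognosis patients" are compared only with each other. The examples are baseline markers (age, Ct value, virus type, time since symptom onset); other randomised allocations are not among them. The exact prognostic factors for these "analyses will be provided in the SAP prior to any unblinded analyses being done".

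**The concern.** Both reasons in section 4.1.2 apply to a co-randomised treatment that lowers mortality. It is a predictor of death, it is recorded without error for every patient, and it is not among the minimisation factors in section 3.3 (age stratum, viral load, outbreak), so the stated scheme does not balance it. In a logistic model, leaving out a predictor pulls the odds ratio towards 1 even when the arms are perfectly balanced, because odds ratios are non-collapsible, and the test loses some power.

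At stake is a small amount of power in every comparison that runs alongside an effective treatment. Section 4.2 expects that some comparisons may fall short of the target size, so power available at little cost is worth having.

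**Working it through.** **Inputs from the protocol.** Section 4.2: about 520 patients per comparison (260 per arm); 50% reference-arm mortality; reductions of one-third (OR 0.50, judged at 2P=0.01) and one-quarter (OR 0.60, judged at 2P=0.05); a prognostic split with control mortality of 30% and 90%. Section 4.1: significance at two-sided 0.05.

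**Assumed, because the documents are silent.** Effects of the other treatments (OR 1, 0.5 or 0.25), no interaction, independent 1:1 allocation, every patient in all three domains, no dropout.

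**The plan's own figures.** The two-proportion formula with pooled variance and 260 per arm gives 90.3% power at 2P=0.01 for 50% vs 33.3%, and 82.1% at 2P=0.05 for 50% vs 37.5%. Both agree with section 4.2.

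**One case by hand: tested OR 0.5, two other treatments at OR 0.5, no prognostic split.**
- Reference-arm mortality by co-allocation (neither, one, the other, both): 66.7%, 50%, 50%, 33.3%; mean 50%.
- Halving the odds in each cell gives 50%, 33.3%, 33.3%, 20%; mean 34.2%.
- Ignoring co-allocation: OR = 0.3417/0.6583 = 0.519. SE = sqrt[1/(260 × 0.25) + 1/(260 × 0.3417 × 0.6583)] = 0.1802. z = 0.656/0.1802 = 3.64. Power at 2P=0.01 = Φ(3.64 − 2.576) = 85.6%.
- Adjusting: OR = 0.500. Each of the four cells has 65 patients per arm and information 65 × v0·v1/(v0+v1), where v = p(1−p). The sum is 65 × (0.1176 + 0.1176 + 0.1176 + 0.0930) = 29.0, so SE = 0.1857. z = 0.693/0.1857 = 3.73. Power = Φ(3.73 − 2.576) = 87.6%.

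The SE rises. The power gain comes from the log odds ratio growing proportionately more. The squared test statistic rises by 5.2%, equivalent to about 0.052 × 520 = 27 more patients.

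**All scenarios** (large-sample logistic regression, N=520, power ignoring / adjusting, %). The split rows add a prognostic term with the log-odds gap between 30% and 90% (2.20 + 0.85 = 3.04), centred so that mean reference mortality stays at 50%.

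| Prognostic split | Other treatments | Tested OR 0.5, 2P=0.01 | Tested OR 0.5, 2P=0.05 | Tested OR 0.6, 2P=0.05 |
|---|---|---|---|---|
| No | inactive | 89.6 / 89.6 | 97.0 / 97.0 | 81.7 / 81.7 |
| No | one at 0.5 | 87.6 / 88.6 | 96.2 / 96.6 | 79.5 / 80.6 |
| No | two at 0.5 | 85.6 / 87.6 | 95.3 / 96.2 | 77.4 / 79.6 |
| No | one at 0.25 | 80.8 / 85.4 | 93.1 / 95.2 | 72.6 / 77.2 |
| Yes | inactive | 65.7 / 65.7 | 84.6 / 84.6 | 60.0 / 60.0 |
| Yes | one at 0.5 | 64.9 / 65.9 | 84.1 / 84.7 | 59.4 / 60.2 |
| Yes | two at 0.5 | 64.1 / 66.0 | 83.6 / 84.8 | 58.8 / 60.3 |
| Yes | one at 0.25 | 62.6 / 66.4 | 82.6 / 85.1 | 57.8 / 60.7 |

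The lower level of the split rows is not a cost of adjusting. An OR of 0.5 within strata of 17.9% and 82.1% lowers mean mortality only from 50% to 39.7%, a smaller overall effect.

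**Standard error.** It falls in no scenario. With two others at OR 0.5 and the split, it goes from 0.2274 to 0.2319 while the OR goes from 0.513 to 0.500.

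**Simulation check** (4,000 trials per scenario). With the split and two others at OR 0.5, power at 2P=0.01 is 64.8% vs 67.0%. Type I error at the 0.05 level is held both ways: 0.049 and 0.049 at N=520, 0.045 and 0.050 at N=120. At N=120 with inactive co-treatments the extra terms raise the mean SE from 0.508 to 0.517.

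**Chance imbalance.** In the protocol's 60 vs 60 example, the between-arm difference in the proportion given a co-treatment has SD sqrt(0.25/60 + 0.25/60) = 9 percentage points.

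**The case against.** Analysing a factorial at the margins is standard and valid, and nothing in the protocol is contradicted. That stands: a reader might infer that the rule biases the test or the estimate, but type I error is held, and the shift from 0.519 to 0.500 is a change of conditional estimand, not the removal of a bias.

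The word ignore may mean only that arms are pooled over other allocations rather than split into cells, with the covariates left to the SAP. This is plausible but not certain. Section 4.1.2 defers baseline prognostic factors, whereas the instruction on co-allocations stands in the protocol, so an SAP that added them would depart from its literal wording. A clarification is useful on either reading.

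A reader might also infer that precision is being thrown away at no cost. The figures do not support that: the standard error never falls, and the extra terms cost a little in small comparisons. Nor is the loss large in general. A gain of four to five points at 2P=0.01 needs a co-treatment as strong as OR 0.25.

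Finally, the calculation puts every patient in all three domains. The protocol does not: availability, contraindication, a definite indication or prior treatment in the class can remove a patient from a domain (sections 2.2.1, 3.2 and 3.3), and where a licensed monoclonal antibody exists patients would generally not enter that domain. The figures therefore tend to overstate the gain.

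**Conclusion.** The point holds as a small, inexpensive improvement, not as an error. Read literally, section 4.1 leaves known randomised treatments out of a model that already adjusts for predictors of death, against the reasoning of section 4.1.2. At the protocol's own pairings of effect and significance level (OR 0.5 at 2P=0.01, OR 0.6 at 2P=0.05), adjusting gains about 1 point with one other treatment at OR 0.5 and about 1.5 to 2 points with two. For a tested OR of 0.5 at 2P=0.05 the gain is about 1 point or less. It is zero if the other treatments are inactive. These sizes rest on assumed co-treatment effects, no interaction and full participation in all domains.

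**What to change.** Reword the sentence in section 4.1 along these lines: *each main comparison pools patients across the other factorial allocations (main effect), from the adjusted logistic model that also includes the allocation in each other domain (active / no additional treatment / not randomised in that domain).* State that coefficients for domains still open are not displayed, and keep the subgroup analyses by factorial allocation as planned.

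The cost is up to two extra parameters per other domain, with a slight rise in standard error in small comparisons; a slightly different conditional odds ratio; and care that reporting one comparison does not reveal the effect in an open domain, given the blinding rules in sections 4.2.1, 5 and 5.2. No new data are needed.
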